7.14 Specimen Management

Each study site will adhere to the standards of good clinical laboratory practice in accordance with *DAIDS Laboratory Policy*, <https://www.niaid.nih.gov/sites/default/files/laboratorypolicy1.pdf>, *MTN-043 SSP Manual*, <https://www.mtnstopshiv.org/research/studies>, and site SOPs for proper collection, processing, labeling, transport, and storage of specimens to standardize procedures. Specimen collection, testing, and storage at the site laboratories will be documented when applicable using the Laboratory Data Management System (LDMS). In cases where laboratory

results are not available due to administrative or laboratory error, sites are permitted to re-draw specimens. Further, as part of quality control, researchers may need to look at short pieces of non-coding repetitive deoxyribonucleic acid (DNA) sequence (3-7 base pairs) from blood in the event of sample mix-up. This test will only let researchers know the number of times this short segment is repeated and not specific genes or specific sequences of base pairs. This sequence element does not contain any information about genes, therefore researchers will not be able to identify if participants are predisposed to specific diseases or any other genetic information based on this information. This test will be an important tool for distinguishing whether two samples collected at the same or different time points are likely from the same person. The test will only be used as part of a sample investigation with the knowledge of the site in situations where a known or suspected sample mix-up has occurred. No genetic testing (limited or genome-wide) is planned on leftover samples that are stored for the purposes of future research.

7.15 DAIDS Laboratory Oversight

All laboratories participating in DAIDS Sponsored and/or Funded Laboratories in Clinical Trials will adhere to the *DAIDS Laboratory Policy* at <https://www.niaid.nih.gov/sites/default/files/laboratorypolicy1.pdf>.

7.16 Biohazard Containment

As the transmission of HIV and other blood-borne pathogens can occur through contact with contaminated needles, blood, and blood products, appropriate blood and secretion precautions will be employed by all personnel in the drawing of blood and shipping and handling of all specimens for this study as recommended by the U.S. Centers for Disease Control and Prevention (CDC) and National Institutes of Health (NIH). All biological specimens will be transported using packaging mandated by US Code of Federal Regulations (CFR) 42 Part 72. All dangerous goods materials, including diagnostic specimens and infectious substances, must be transported according to instructions detailed in the International Air Transport Association (IATA) Dangerous Goods Regulations. Biohazard waste will be contained according to institutional, transportation/carrier, and all other applicable regulations.

8 ASSESSMENT OF SAFETY

8.1 Safety Monitoring

Site IoRs/designees are responsible for continuous close safety monitoring of all study participants, and for alerting the PSRT if unexpected concerns arise. A sub-group of the Protocol Team, including the Protocol Chair(s), DAIDS MO, NICHD MO, Protocol Safety Physician(s), IPM Representative, and Gilead Representative will serve as the PSRT. The MTN Statistical Data and Management Center (SDMC) prepares routine AE and clinical data reports for review by the PSRT, which meets via conference call approximately once per month or as needed throughout the period of study implementation to review safety data, discuss product use management, and address any potential safety concerns.

8.2 Clinical Data Safety Review

A multi-tiered safety review process will be followed for the duration of this study. The study site Investigators are the first layer of this tiered system and are responsible for the initial evaluation and reporting of safety information at the participant level, and for alerting the PSRT if unexpected concerns arise. Participant safety is also monitored at the Network level through a series of routine reviews conducted by the SDMC staff, the PSRT, and study sponsor.

During the study, the PSRT will review safety reports and conduct calls to review the data once a month. The content and format of the monthly safety reports will be agreed upon by the PSRT and the SDMC in advance of study implementation. In addition to these routine safety data reviews, the PSRT will convene on an ad hoc basis to make decisions regarding the handling of any significant safety concerns. If necessary, experts external to the MTN with expertise in the fields of microbicides, biostatistics, or medical ethics may be invited to join the PSRT safety review.

8.3 Adverse Events Definitions and Reporting Requirements

8.3.1 Adverse Events

An AE is defined as any untoward medical occurrence in a clinical research participant administered an investigational product and which does not necessarily have a causal relationship with the investigational product. As such, an AE can be an unfavorable or unintended sign (including an abnormal laboratory finding, for example), symptom or disease temporally associated with the use of an investigational product, whether considered related to the product. This definition is applied to all study participants at the time of enrollment. This definition is applied to all study groups and is applied beginning at the time of enrollment (i.e., once a participant is randomized). The term “investigational product” for this study refers to the DPV VR and Truvada oral tablet.

Study participants will be provided instructions for contacting the study site to report any untoward medical occurrences they may experience. In cases of potentially life-threatening events, participants will be instructed to seek immediate emergency care. Where feasible and medically appropriate, participants will be encouraged to seek evaluation where a study clinician is based, and to request that the clinician be contacted upon their arrival. With appropriate permission of the participant, whenever possible, records from all non-study medical providers related to untoward medical occurrences will be obtained and required data elements will be recorded on study CRFs. All participants reporting an untoward medical occurrence will be followed clinically until the occurrence resolves (returns to baseline) or stabilizes.

Study site staff will document in source documents and in the study database all AEs reported by or observed in enrolled study participants, regardless of severity and presumed relationship to study product.

AE severity and laboratory tests will be graded per the *DAIDS Table for Grading the Severity of Adult and Pediatric Adverse Events, Corrected Version 2.1, July 2017* and *Addendum 1, (Female Genital Grading Table for Use in Microbicide Studies; dated November 2007)*. In cases where a genital AE is covered in both tables, the *Female Genital Grading Table for Use in Microbicide Studies* will be the grading scale utilized.

The following will not be reportable as AEs:

- Asymptomatic BV and asymptomatic vulvovaginal candidiasis.
- Bleeding at the time of speculum insertion/removal or cervicovaginal specimen collection that is judged by the clinician to be within the range normally anticipated for that procedure; however, bleeding of greater quantity or longer duration than typical will still be reported.
- Weight loss that is judged by the clinician to be within the range normally anticipated in the postnatal period.
- Vaginal bleeding that is judged by the clinician to be within the range normally anticipated in the postnatal period.

For any serious or expedited adverse events (EAEs) that are continuing at a participant's study exit visit, the IoR/designee must establish a clinically appropriate follow-up plan for the AE. At a minimum, the SAE or EAE must be re-assessed by study staff 30 days after the participant's study exit visit; additional evaluations also may take place at the discretion of the IoR/designee. The same approach must be taken for any AEs that are found to have increased in severity at the study exit visit, or any new \geq Grade 3 AEs identified at the last visit. For those AEs requiring re-assessment, if the AE has not resolved or stabilized at the time of re-assessment, study staff will continue to re-assess the participant at least once per month while the study is ongoing. After the study has ended, all AEs requiring re-assessment will be re-assessed at least once within the 30-60 days after the study end date. The PSRT may advise study staff as to whether any additional follow-up may be indicated on a case by case basis. For AEs that are re-assessed after study exit, information on the status of the AE at the time of re-assessment will be recorded in source documents only — no updates should be made to AE Log CRFs based on the re-assessments.

8.3.2 Serious Adverse Events

SAEs will be defined by the *Manual for Expedited Reporting of Adverse Events to DAIDS (Version 2.0, January 2010)*, as AEs occurring at any dose that:

- Result in death
- Are life-threatening
- Require inpatient hospitalization or prolongation of existing hospitalization
- Result in persistent or significant disability/incapacity
- Are congenital anomalies/birth defects
- Are important medical events that may not result in death, be immediately life-threatening, or require hospitalization but may jeopardize the participant or require intervention to prevent one of the outcomes listed in the definition above

8.3.3 Adverse Event Relationship to Study Product

Relatedness is an assessment made by a study clinician of whether the event is related to the study agent. Degrees of relatedness will be categorized according to current DAIDS-approved Guidelines. Per the *Manual for Expedited Reporting of Adverse Events to DAIDS (Version 2.0, January 2010)*, the relationship categories that will be used for this study are:

- *Related*: There is a reasonable possibility that the AE may be related to the study agent
- *Not Related*: There is not a reasonable possibility that the AE is related to the study agent

8.4 Expedited Adverse Event Reporting Requirements

8.4.1 Adverse Event Reporting to DAIDS

Requirements, definitions and methods for expedited reporting of AEs are outlined in Version 2.0 of the *DAIDS EAE Manual*, which is available on the Regulatory Support Center (RSC) website at <https://rsc.niaid.nih.gov/clinical-research-sites/manual-expedited-reporting-adverse-events-daims>. For each study participant, EAE reporting will be undertaken throughout the scheduled duration of follow-up, i.e., from the time of Enrollment through study termination.

The DAIDS Adverse Experience Reporting System (DAERS), an internet-based reporting system, must be used for EAE reporting to DAIDS. In the event of system outages or technical difficulties, EAEs may be submitted via the *DAIDS EAE Form*. For questions about DAERS, please contact the National Institute of Allergy and Infectious Diseases (NIAID) Clinical Research Management System (CRMS) Support at [contact]. Site queries may also be sent from within the DAERS application itself.

The DAIDS EAE form is available on the RSC website, <https://rsc.niaid.nih.gov/clinical-research-sites/paper-eae-reporting>.

For questions about EAE reporting, please contact the RSC ([contact]).

8.4.2 Reporting Requirements for this Study

The SAE Reporting Category, as defined in Version 2.0 of the *DAIDS EAE Manual*, will be used for this study. The study agents requiring expedited reporting are the dapivirine vaginal ring (DPV VR) and Truvada oral tablet.

8.4.3 Grading Severity of Events

The grading of severity of events and the reporting period will be the same as for all AEs, as described in [Section 8.3.1](#). The *DAIDS Table for Grading the Severity of Adult and Pediatric Adverse Events, Corrected Version 2.1, July 2017* and the *Female Genital Grading Table for Use in Microbicide Studies (Addendum 1, dated November 2007)*, will be used and are available on the RSC website at <https://rsc.niaid.nih.gov/clinical-research-sites/daims-adverse-event-grading-tables>.

8.4.4 Expedited Adverse Event Reporting Period

The EAE reporting period for this study begins once the participant is enrolled and continues up through the participant's final study visit. After the protocol-defined AE reporting period, unless otherwise noted, only suspected, unexpected serious adverse reactions (SUSARs) as defined in Version 2.0 of the *EAE Manual* will be reported to DAIDS if the study staff become aware of the events on a passive basis (from publicly available information).

8.5 Social Harms Reporting

Although study sites will make every effort to protect participant privacy and confidentiality, it is possible that participants' involvement in the study could become known to others and that social harms – non-medical adverse consequences – may result. For example, participants could be

treated unfairly, or could have problems being accepted by their families, partners and/or communities. Social harms that are judged by the IoR/designee to be serious or unexpected will be reported to the PSRT and responsible site IRBs/ECs according to their individual requirements beginning at the time of enrollment (i.e., after a participant signs the informed consent and eligibility is confirmed) until study participation is complete. If a participant reports social harm, every effort will be made by study staff to provide appropriate care and counseling to the participant, and/or referral to appropriate resources for the safety of the participant as needed. Each site will provide such care and counseling in accordance with standardized guidance provided in the *MTN-043 SSP Manual*. While maintaining participant confidentiality, study sites may engage their community advisory boards (CABs) in exploring the social context surrounding instances of social harm.

8.6 Regulatory Requirements

Information on all reported CRFs will be included in reports to the FDA and other applicable US, local and international government and regulatory authorities. Site IoRs/designees will submit AE information in accordance with local regulatory agencies' or other local authorities' requirements. Site IoRs/designees also will submit AE information and any other relevant safety information to their IRBs/ECs in accordance with IRB/EC requirements.

9 CLINICAL MANAGEMENT

Guidelines for clinical management and temporary product hold/permanent discontinuation of study product are outlined in this section. In general, the IoR/designee has the discretion to hold study product temporarily at any time if s/he feels that continued product use would be harmful to the participant or interfere with treatment deemed clinically necessary. Unless otherwise specified below, the IoR/designee should immediately consult the PSRT for further guidance on resuming study product, continuing the hold temporarily, or progressing to permanent discontinuation of study product. The IoR/designee will document all temporary product holds and permanent discontinuations on applicable CRFs.

9.1 Grading System

AE severity grading is described in [Section 8.3.1](#).

9.2 Dose Modification Instructions

No dose modifications will be undertaken in this study.

9.3 General Criteria for Temporary/Permanent Discontinuation of Study Product

Participants will be permanently discontinued from study product by the IoR/designee for any of the following reasons:

- Acquisition of HIV-1 infection.
- Acquisition of hepatitis B infection (for Truvada group only).
- Confirmation of \geq Grade 2 creatinine clearance (for Truvada group only).
- Confirmation of \geq Grade 2 glycosuria or proteinuria (for Truvada group only).
- Allergic reaction to the study product.

- Reported use of PrEP for HIV prevention outside of the study.
- Reported use of PEP for potential HIV exposure.
- Non-therapeutic injection drug use.
- Pregnancy.

A participant will be temporarily held from study product for any of the following reasons:

- A reactive rapid HIV test. The study product must be held beginning immediately upon recognition of the first reactive rapid HIV test. If, via the algorithm in [Appendix IV](#), the participant is determined to be HIV-uninfected, she may resume product use. The IoR/designee must permanently discontinue the study product if HIV-1 infection is confirmed.
- Participant is unable or unwilling to comply with required study procedures, or otherwise might be put at undue risk to her/her infant's safety and well-being by continuing product use, according to the judgment of the IoR/designee. The IoR/designee must consult the PSRT on all temporary product holds instituted for this reason for further guidance on resuming product use, continuing the temporary hold, or progressing to permanent discontinuation. If product use is temporarily held/permanently discontinued for this reason, but the underlying reason for the temporary hold later resolves, the IoR/designee should consult the PSRT to resume product use at that time.

9.4 Temporary Product Hold/Permanent Discontinuation in Response to Observed Adverse Events

Study product may be held per IoR/designee discretion for any reason. In these instances, the IoR/designee should notify the PSRT.

The following outlines product use considerations for observed adverse events. Except for deep epithelial disruption, study product use will depend on the adverse event grade and relations to study product.

Deep epithelial disruption (ulceration)

- Temporarily hold study product for deep epithelial disruption confirmed by site investigator.
- Re-evaluate in 3-5 days and resume study product use if resolved.
- If unresolved at 3-5 days, re-evaluate within 2-3 days. If resolved at that time, may resume study product use. If unresolved at this second reevaluation, continue temporary product hold, consult with PSRT regarding permanent discontinuation, and provide care per local standard.
- If there is reoccurrence with no identified etiology, continue temporary product hold and consult the PSRT regarding permanent discontinuation.

Grade 1 or 2

In general, a mother or infant who develops a Grade 1 or 2 AE, regardless of relatedness to study product, may continue product use.

Grade 3

Mothers who develop a Grade 3 AE that is judged by the IoR/designee to be not related to study product may continue product use.

In general, for mothers who develop a Grade 3 AE judged by the IoR/designee to be related to study product, and unless otherwise decided in consultation with the PSRT, the IoR/designee should:

- Temporarily hold the study product.
- Re-evaluate the participant at least weekly for up to two weeks.
- Resume study product if improvement to \leq Grade 2 is documented within two weeks.
- Consult PSRT regarding further study product management if improvement to severity \leq Grade 2 cannot be documented within two weeks.

If product use is resumed and the same Grade 3 AE deemed related to study product recurs at any time, the IoR/designee must temporarily hold study product and consult the PSRT for further guidance on continuing the temporary hold or progressing to permanent discontinuation of the study product.

Mothers whose infant develop a Grade 3 AE (regardless of relationship to study product) should have their study product held. The IoR/designee must consult the PSRT and continue the temporary product hold until a recommendation is obtained from the PSRT.

Grade 4

Mothers who develop a Grade 4 AE (regardless of relationship to study product) should have the study product held. The IoR/designee must consult the PSRT and continue the temporary product hold until a recommendation is obtained from the PSRT.

Mothers whose infant develop a Grade 4 AE (regardless of relationship to study product) should have their study product held. The IoR/designees must consult the PSRT and continue the temporary product hold until a recommendation is obtained from the PSRT.

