	Blood	
 • HIV-1 testing • AST/ALT • Creatinine clearance • CBC with platelets • Syphilis serology* • Plasma for DPV drug levels (DPV group) • DBS for FTC-TP & TFV-DP drug levels (Truvada group)

Early Termination Visit - Mothers		
Component		Procedures
	Breast milk	
 • Breast milk for DPV drug levels (DPV group) • Breast milk for FTC & TFV drug levels (Truvada group)
	Pelvic	
 • NAAT for GC/CT/TV* • Wet prep/KOH wet mount for candidiasis and/or BV* • Vaginal pH* • Vaginal swab(s) for microbiota • Vaginal Gram stain • Vaginal swab(s) for biomarkers
	Study Product	
 • Adherence assessment: Returned study VR
Study Product/Supplies		
 • Removal and collection of study VR or unused study tablets • Offer male condoms

* If indicated and/or per local standard of care

Table 16: Early Termination Visit - Infants

Early Termination Visit - Infants		
Component		Procedures
Clinical		
 • Review/update medical history • Review pediatric care records • Review/update concomitant medications • Targeted physical exam • Collect AEs
Laboratory	Blood	
 • Plasma for DPV drug levels (DPV group) • DBS for FTC-TP & TFV-DP drug levels (Truvada group)

7.5 Follow-up Procedures for Participants Who Temporarily Hold or Permanently Discontinue Study Product

Participants who permanently discontinue study product use due to an AE must continue to be followed until resolution or stabilization of the AE is documented.

Guidance related to temporary and permanent discontinuation of study product, including additional information regarding consultation with the PSRT, is included in [Section 9.3](#).

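### Protocol 9.4 names deep epithelial disruption as its only exception, so read alone it contradicts the mandatory permanent-stop criteria in 9.3

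*Protocol*

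**What the plan says.** Protocol Section 9.3 opens its list of permanent-stop criteria with "Participants will be permanently discontinued from study product by the IoR/designee for any of the following reasons". One of the nine criteria is "Allergic reaction to the study product", with no grade threshold and no confirmation step. Two others apply to the Truvada group only: confirmed Grade 2 or higher creatinine clearance, and confirmed Grade 2 or higher glycosuria or proteinuria. Neither depends on relatedness.

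Section 9.4, on product use after observed adverse events, states its rule as "Except for deep epithelial disruption, study product use will depend on the adverse event grade and relations to study product". It does not mention 9.3. For mothers at Grade 3 it has two branches:

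- Judged unrelated: "Mothers who develop a Grade 3 AE that is judged by the IoR/designee to be not related to study product may continue product use".
- Judged related: in general, and unless the PSRT decides otherwise, hold product, re-evaluate at least weekly, and resume if improvement to at or below "Grade 2 is documented within two weeks". PSRT consultation is called for if that improvement is not documented in time, or if the same event recurs after resumption.

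The Section 9 introduction sets a default: "Unless otherwise specified below, the IoR/designee should immediately consult the PSRT for further guidance on resuming study product". By its own first words, that default gives way to anything more specific later in the section.

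**The concern.** For the same event, the two adjacent sections can give different instructions, and neither is said to outrank the other. 9.3 is headed as general criteria. 9.4 is headed as the response to observed adverse events, so staff managing an event would naturally turn to it, and naming one exception suggests there are no others.

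What is at stake is participant safety. Protocol Section 13.4.1 says an allergic reaction to the ring is possible, gives difficulty in breathing among its symptoms, and lists allergic reaction and kidney damage among the rare but serious Truvada effects. A site that followed 9.4 alone could restart product in a mother whom 9.3 says must stop for good.

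**Working it through.** No figure in the plan needs reproducing. The check runs each overlapping event through both sections.

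**Overlap.** Three of the nine criteria in 9.3 are findings that would ordinarily be graded as adverse events: allergic reaction (both arms, about 200 mothers planned) and the two renal or urinary criteria (Truvada arm, about 50).

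**Comparison.**

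| Event | 9.3 | 9.4 read alone | Result |
|---|---|---|---|
| Grade 3 allergic reaction to product | Permanent stop | Hold; resume at Grade 2 or below within two weeks, unless the PSRT decides otherwise | Conflict |
| Truvada, confirmed Grade 3 renal/urinary finding, unrelated | Permanent stop | May continue, no qualifier | Conflict |
| Same finding, related | Permanent stop | Hold; may resume at Grade 2, itself a stop level in 9.3 | Conflict |
| Truvada, Grade 3 renal/urinary result not yet confirmed | Not triggered | Hold and re-evaluate if related; may continue if unrelated | No conflict |
| Grade 1 or 2 event meeting a 9.3 criterion | Permanent stop | In general, may continue | Weaker: hedged wording |
| Grade 4 event meeting a 9.3 criterion | Permanent stop | Hold until the PSRT advises | Weaker: no automatic resumption |

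**Is precedence stated elsewhere?** The Section 9 introduction, 6.5 with Table 2, 7.5, 9.5, and SAP 6.3 and 10.2 contain no sentence ranking 9.3 over 9.4. Some of them do show intent:

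- Table 2 gives a retrieval time for permanent discontinuation due to Grade 3 or higher renal toxicity.
- SAP 6.3 lists allergic reaction among the collected reasons for not completing product. It does not list the renal criteria separately; those would fall under adverse event or other.
- Section 7.5 points the reader to 9.3 for discontinuation guidance.

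**How often could the trigger arise?** These figures concern the triggering event, not a wrongful restart.

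- *Ring.* Section 2.7.3 reports product-related events as all Grade 1 in one Phase 3 trial and all Grade 2 in the other; Section 2.7 gives 2620 women assigned the ring. At face value, that is 0 related Grade 3 events in 2620. The exact two-sided 95% upper bound is u = 1 − 0.025^(1/2620) = 0.14%. Among 150 mothers, the expected number is at most 150u = 0.21, and the chance of at least one is at most 1 − (1 − u)^150 = 19.0%. This covers any related Grade 3 ring event. It is conservative also because women in those trials used the ring for a year or more, against 12 weeks here.
- *Truvada.* Section 13.4.1 calls the relevant effects rare but gives no rate. Assuming p = 0.1% to 0.5% for each type of event, the expected number among 50 mothers is 50p = 0.05 to 0.25, and the chance of at least one is 1 − (1 − p)^50 = 4.9% to 22.2%.

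**Extra exposure if product were wrongly resumed.** With 12 weeks of use and a one- to two-week hold, this is 12 − (week found + hold):

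- found at Week 1: 12 − 2 to 12 − 3, or 10 to 9 weeks
- found at Month 2 (week 8): 12 − 9 to 12 − 10, or 3 to 2 weeks
- found at the Month 3 product-use-end visit: none

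**The case against.** The strongest reply is that 9.3 plainly comes first. It says participants will be stopped for any listed reason, while 9.4 mostly uses softer terms (may, should, in general), and once product has been permanently stopped there is nothing to resume. Pressed literally, the conflict also reaches too far: newly acquired hepatitis B is a disease too, and nobody would suppose 9.4 lets a Truvada mother continue because it was judged unrelated. The natural reading is that 9.3 is applied first and 9.4 covers the remaining events. This largely stands, and it defeats a stronger inference a reader might draw, that the protocol permits or intends restarting product after a mandatory-stop event. Taken as a whole, the documents do not support that.

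A reader might also infer that the PSRT is bypassed. That goes too far. The related Grade 3 branch allows the PSRT to decide otherwise, 9.3 requires PSRT consultation when product is held because continuing might put the mother at undue risk, and the PSRT reviews safety data about monthly. What remains is narrower: where improvement is documented in time, the 9.4 steps do not require consultation before product is resumed.

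The renal case has little practical reach. Mothers with Grade 1 or higher creatinine or creatinine clearance at screening are excluded, routine clearance testing after enrollment falls at the product-use-end or early termination visit, when product is collected, and the urine dipstick is done only if indicated or per local standard of care.

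Section 13.3 assigns adverse event management guidance to the study-specific procedures manual, which is not among the documents and may state the order of application. Even if it does, the protocol sentence would still be wrong as printed.

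**Conclusion.** The concern holds as an internal inconsistency in a safety rule. 9.4's single named exception is incomplete, and applied alone the section gives the wrong action for a Grade 3 allergic reaction in either arm and for a confirmed Grade 3 renal or urinary finding in a Truvada mother. The allergic reaction case is the more important; the renal case is narrow.

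The size is small and cannot be put as a rate of harm. A reader might take the 19.0% or the 4.9% to 22.2% as the chance of wrongful re-exposure. The documents do not support that: the first is an upper confidence limit on any related Grade 3 ring event, based on summary statements taken at face value; the second rests on assumed rates; and neither allows for the probability that a site would follow 9.4 over 9.3, for which there is no figure.

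The primary safety analyses are essentially unaffected. SAP Sections 3.1, 8.1 and 8.2 classify participants by randomized arm and count each once. The reason to act is that a rule on re-exposure should not need to be inferred, and the correction is trivial.

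**What to change.** Replace the opening exception of the 9.4 sentence with: *Except for events meeting a permanent-discontinuation criterion in Section 9.3, which takes precedence over the guidance below regardless of grade or relatedness, and except for deep epithelial disruption*. Keep the rest of the sentence, correcting relations to relationship. This also settles the weaker Grade 1–2 and Grade 4 mismatches, and leaves sites free to hold product while a renal result is being confirmed.

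The cost is one clause in a clarification memo or letter of amendment, with no added procedures, visits or analyses. The procedures manual should be checked for matching wording.
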